The goal of this study is to evaluate the efficacy of a Brief Early Intervention (BEI) for reducing early alcohol and marijuana use in a group of adolescents (age 12-16) with ADHD who are at elevated risk for substance use problems. All adolescents will receive the BEI (based upon Teen Intervene). The Brief Early Intervention (BEI; 5 individual sessions with adolescent with some parent involvement during 3 of these sessions) will consist of a modification of a brief early intervention program designed by Winters (Winters & Leitten, 2007) with the addition of enhanced decision making skills. Due to the existing support for the intervention, the criterion for eligibility (elevated risk factors for early initiation of substance use), and concern for randomizing families with adolescents at risk for worsening substance use outcomes into a control (no treatment) condition for one to two years, no control condition is used in the current design at the first level of intervention. Similarly, due to the time required to see a potential effect of the treatment (6 months post-brief intervention), a wait-list control condition was not considered.

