The initial part of the study design is to evaluate the effectiveness of the brief early intervention for substance use. Analyses will be based upon measures of substance use and ADHD symptoms, measured at baseline and 6 month assessments. The analytical plan addresses the multiple measurements on the same participant, with a cautious eye toward any concerning missing data issues. We expect drop out to be minimal as has been the case in our decade of experience with treatment studies of ADHD teens. To date, our collective dropout rate is below 5% per year. *Studies conducted in Miami-Dade County with Hispanic adolescents who display behavior problems and emergent substance use report slightly lower retention, with 16-19% attrition (Pantin et al., 2009; Prado et al., 2007). In our studies, data loss has also been relatively low; should there be a missing data issue, we suspect that the last observation carried forward method (LOCF) will be a satisfactory strategy to use. However, we are well aware of other methods and would also use the Mixed-Effects Model Repeated Measures (MMRM) which is more robust to biases and provides better control on type I and II error.*

A careful assessment of data quality will be undertaken as data are being collected and entered, with the usual set of appropriate value, range and logic checks. Data will be collected and handled in a manner that satisfies all local and national requirements for personal privacy, specifically PHI, and data security. Prior to analyzing outcome, comprehensive assessments of data quality, including examination of requirements for the assumptions underlying outcome analyses (i.e., normality, linearity, independence, homogeneity of variance) will be undertaken. Should these assumptions not be met, we will adjust the analytical approach or use transformations as appropriate. We will also apply standard methods for outlier detection (e.g., analysis of leverage statistics, residuals, and df Betas), and use robust statistical significance tests if variance is heterogeneous or re-specify model terms if assumptions of linearity are violated.

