Aim 1: The first aim is to test whether individuals' substance use outcomes decrease significantly from baseline to 6-month assessment. We will calculate days of alcohol and marijuana use during the past 90-days using data from the Substance Use Questionnaire. We will also examine quantity of alcohol use gathered from the SUQ. Repeated measures GLM techniques as implemented by SAS PROC GLM will be used. Several control variables (age, ethnicity, family SES, gender, and functional impairment associated with ADHD) will be entered into the model as covariates. As a secondary analysis, we will also examine % of participants at each

randomization point (6-months, 9 months, 12 months, 15 months, 18 months) who continue to maintain normative use in a time until they stop context. For these analyses, we expect to use Cox Proportional Hazards Regression techniques.

Aim 2: The second aim of this study is to test whether situational, proximal, and cognitive variables listed above predict response to the BEI. At this stage of the study, we will investigate whether each secondary outcome (see Table 5) is a significant predictor of treatment response. Using the GLM as described above, we will investigate the impact of the covariates on substance use variables over time. Predictors will be entered in to the model simultaneously, so long as our sample size adequately supports such inclusion. Should the Cox Regression model, which measures timing, provide a more sensitive measure of substance use trajectories, we will include moderator terms in this model as well.

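### Aim 1 rests on PROC GLM with LOCF called satisfactory for missing data; the MMRM that the plan itself calls more robust should be primary, with a sensitivity analysis for use-related dropout

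*Combined protocol and SAP*

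**What the plan says.** The only missing-data rule is in the opening text of Analyses, under Hypotheses and Data Analysis. It is conditional: "should there be a missing data issue, we suspect that the last observation carried forward method (LOCF) will be a satisfactory strategy to use". The next sentence turns to MMRM, "which is more robust to biases and provides better control on type I and II error", and says it would be used as well. The text does not say which method is primary or what follows if they disagree.

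The Aim 1 paragraph asks whether substance use outcomes "decrease significantly from baseline to 6-month assessment" and fixes the model: "Repeated measures GLM techniques as implemented by SAS PROC GLM will be used". It gives no missing-data rule.

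Two design features matter. The Aim 1 measures are "measured at baseline and 6 month assessments", so there are two time points. Research Design and Methods states that "no control condition is used in the current design at the first level of intervention".

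On expected loss, Analyses reports that "our collective dropout rate is below 5% per year", and that local studies in a similar population "report slightly lower retention, with 16-19% attrition". The Power Analysis paragraph plans for a maximum of 15%.

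**The concern.** With two time points, carrying the last value forward means carrying baseline forward, so every dropout enters as exactly no change. Without imputation, PROC GLM's usual handling of repeated measures drops any teen with no 6-month value. That is software behaviour; the plan does not state it. Either way, the baseline information on dropouts is not used to adjust the 6-month mean, which is what a likelihood-based mixed model does.

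With no control arm, any resulting bias goes straight into the reported change and cannot cancel between groups. Loss related to use is plausible: the risk-factor criteria under Participants admit both users and non-users, so baseline use will vary, and Potential Risks warns that motivation may be low at first among substance users. If lighter users leave, the bias produces an apparent fall in use, which is the result Aim 1 hopes to see. If heavier users leave, a real fall is understated.

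**Working it through.** **Inputs.** From Power Analysis: N = 300, two-sided alpha 0.05, effect 0.25 SD, stated power 0.96 without loss and 0.90 with 15% loss. The correlation r = 0.25 is stated there for the medication interaction; using it for the main Aim 1 test is an assumption. The gap g (dropout minus completer baseline mean, in SD) is not in the documents. I take ±0.5 and ±0.25. Below, d is the fraction lost.

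**1. The plan's own figure.** Paired t-test with standardised change 0.25/√(2(1 − 0.25)) = 0.204. Power is 0.941 at n = 300 (stated 0.96) and 0.901 at n = 255 (stated 0.90). The second matches and the first is 0.019 low, so r = 0.25 is a reasonable working value.

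**2. Random loss.** Complete-case and likelihood estimates average 0.25. LOCF gives (1 − d) × 0.25:
- 5% loss: 0.95 × 0.25 = 0.2375
- 15% loss: 0.85 × 0.25 = 0.2125
- 19% loss: 0.81 × 0.25 = 0.2025

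Simulated power at 15% loss is 0.904 (complete-case), 0.904 (LOCF) and 0.921 (likelihood), so here the cost is in the estimate rather than the test.

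**3. Loss depending on baseline use.** Completers' baseline mean is off by −d·g and their 6-month mean by −r·d·g. So:
- complete-case fall = 0.25 − (1 − r)·d·g
- LOCF fall = (1 − d) × that
- the likelihood model uses all baselines and regression-adjusts the 6-month mean, which removes the shift

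| d | r | g | Complete-case | LOCF | Likelihood |
|---|---|---|---|---|---|
| 15% | 0.25 | +0.5 (heavier leave) | 0.25 − 0.75×0.15×0.5 = 0.194 | 0.165 | 0.250 |
| 15% | 0.25 | −0.5 (lighter leave) | 0.306 | 0.260 | 0.250 |
| 15% | 0.25 | +0.25 | 0.222 | 0.189 | 0.250 |
| 15% | 0.25 | −0.25 | 0.278 | 0.236 | 0.250 |
| 15% | 0.5 | +0.5 | 0.212 | 0.181 | 0.250 |
| 15% | 0.5 | −0.5 | 0.287 | 0.244 | 0.250 |
| 5% | 0.25 | +0.5 | 0.231 | 0.220 | 0.250 |
| 5% | 0.25 | −0.5 | 0.269 | 0.255 | 0.250 |

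**4. False positives with no true change.** At 15% loss the standard error is √(1.5/255) = 0.0767.
- g = ±0.5: bias 0.056, ratio 0.733. Rejection = P(Z > 1.227) + P(Z < −2.693) = 0.110 + 0.004, about 11%. Simulation gives 0.112 to 0.116, against 0.048 to 0.053 for the likelihood model.
- g = ±0.25: bias 0.028, ratio 0.367, rejection about 6.6% (simulated 0.063 to 0.069).
- 5% loss, g = ±0.5: bias 0.019, standard error √(1.5/285) = 0.0725, rejection about 5.8% (simulated 0.055 to 0.057).

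LOCF and complete-case reject alike. LOCF multiplies the mean change m by (1 − d) and, for small changes, its standard error becomes s√((1 − d)/n), where s is the SD of change. Hence t = m√(n(1 − d))/s, the complete-case statistic.

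**5. Loss depending on unseen 6-month use** (heavier users leave, 15% loss, true fall 0.25, simulated; complete-case, LOCF, likelihood):
- log-odds slope 0.5 per SD: 0.304, 0.258, 0.317
- slope 1: 0.350, 0.298, 0.376
- slope 1 with no true change: rejection 0.257, 0.257, 0.396

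The likelihood model is furthest from the truth. LOCF is nearest only because its shrinkage toward zero offsets the selection bias. At 15% loss, shifting dropouts by 0.5 SD moves the likelihood estimate by 0.15 × 0.5 = 0.075, so removing the slope-1 bias of 0.126 takes 0.126/0.15 = 0.84 SD.

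**6. Shape of the outcome.** Steps 2 to 5 assume normality, but days of use in 90 will contain many zeros. A simulation with no true change, 60% zeros and about 15% loss (30% of users, 5% of non-users) gave rejection of 9.3%, 9.3% and 7.3%, with estimated changes of +0.30, +0.26 and −0.09 days.

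**The case against.** The strongest reply is that the plan already judges MMRM the better method, makes LOCF conditional on a missing-data problem, and expects so little loss that the choice hardly matters. Much of that stands. The text does rank the two on merit; what it omits is the primary designation. At 5% loss the differences are at most about 0.03 SD, and Aim 1 ends at 6 months after treatment, so on the centre's own record the problem is small. But 15% is the plan's own planning maximum, and the local studies it cites ran at 16-19%.

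It can also be said that a 0.5 SD gap is hard to reach in the direction of lighter users, because use cannot fall below zero. Further zero-heavy simulations bear this out: with non-users leaving three times as often, the gap was 0.22 to 0.31 SD and complete-case and LOCF rejected 5-7%. Only when essentially all dropouts were non-users did rejection reach 9-12%. In the same direction, LOCF at the planned effect lands near the truth (0.24 to 0.26), by offsetting errors.

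Finally, the recommended model has limits. It is the worst of the three in step 5, and when users left three times as often with r above 0.5, a linear MMRM rejected 7-10% against 5-7% for the others. This stands too. It is why the fix asks for a model form suited to the counts and a sensitivity analysis, and not simply a switch to MMRM.

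**Conclusion.** The point holds as a correction the sponsor should make. The named Aim 1 model and the method called satisfactory for missing data either delete dropouts or score them as unchanged, while a method the plan describes as more robust is left without a primary role. LOCF's shrinkage under random loss (0.25 to about 0.21 at 15%) needs no assumption beyond the loss rate. The bias under baseline-related loss, and the 11% against 5% rejection, rest on 15% loss, a 0.5 SD gap, r = 0.25 borrowed from another test, and a normal outcome. A 0.25 SD gap gives 6-7%, and loss below 5% makes the issue minor.

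A reader might infer four stronger things that are not supported:
- **That the false-positive rate will double.** This depends on a gap and direction the documents do not give. If heavier users leave, the spurious change is an increase, against the Aim 1 hypothesis.
- **That LOCF is worse than complete-case GLM for false positives.** The two reject alike; the contrast is with the likelihood model.
- **That MMRM removes dropout bias.** It handles loss explained by the observed data, and not loss driven by unseen 6-month use.
- **That Aim 3 shares the fault.** The plan does not say LOCF applies there, and no error has been shown, so no change to Aim 3 is claimed.

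**What to change.** In the opening Analyses text and the Aim 1 paragraph:

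- Name one likelihood-based mixed model on all observed baseline and 6-month values as the primary Aim 1 analysis in place of PROC GLM. Keep the covariates already listed for Aim 1, and choose a form suited to zero-heavy day counts.
- State that LOCF is not used for the primary result.
- Add one sensitivity analysis for loss related to unobserved use: multiple imputation with a delta shift toward heavier use in dropouts, for example from 0 to 1 SD. That range covers the 0.84 SD in step 5.

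The cost is a change of SAP wording and slightly more programming. No new data are needed.

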Adolescents will be evaluated for treatment non-response to the BEI at 6, 9, 12, 15, and 18 months posttreatment. Non-response is defined as non-normative use of alcohol, marijuana, or other drugs in the past 90 days. Alcohol and marijuana are the outcomes of interest in this study; however, non-normative use of any psychoactive substance will be considered non-response. Alcohol use norms by age are presented in Table 4 and any marijuana use in adolescence is considered non-normative (NHSDAH, 2007). Tobacco and caffeine products are excluded from consideration. For alcohol, marijuana, and other drugs, frequency and quantity of substance use will be collected for the past 90-days using the Substance Use Questionnaire (SUQ). Adolescents who do not demonstrate a response to the BEI at the 6, 9, 12, 15, or 18 month assessment (i.e., use substances at non-normative levels) will be randomized to either (1) No Additional Treatment Monitoring Group, (2) Parent Training/Adolescent CBT (PT/ACBT; e.g., 12 weeks of parent training and adolescent CBT) (3) PT/ACBT plus concurrent stimulant medication (PT/ACBT+MED). Adolescents who demonstrate immediate initial response will be released from treatment and assigned to a monitoring condition in which they are reassessed at 9, 12, 15, and 18 months. Any adolescent who demonstrates non-normative use at any of the follow-up assessments as defined above will be immediately eligible for randomization to further treatment (as detailed above). Adolescents and parents will complete an assessment battery at the randomization point as outlined in Table 5 unless randomization occurs immediately following the 6 or 12 month assessment (in which case the measures will not need to be repeated).

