Aim 1: We will investigate response to a brief early intervention (BEI) for substance use among adolescents with ADHD. We hypothesize that approximately 50% of adolescents will show meaningful response to the BEI, as evidenced by no more than normative substance use assessed at 6-months following treatment. Aim 2: We will also test whether key variables associated with ADHD (ADHD symptoms) and with the development of substance use (parental monitoring, social impairment, academic functioning, family conflict, deviant peer affiliation and peer drug use, risky sexual behavior, delinguency, teen motivation and selfefficacy) predict response to the BEI. It is expected that poor response to treatment will be associated with high ADHD symptomatology, concurrent delinquency, risky sexual behavior, deviant peer affiliations, academic impairment, family conflict, lack of parent monitoring, poor self-efficacy and high motivation to use substances. Aim 3: We will also examine relative efficacy between the randomized second level interventions for BEI nonresponders (i.e., no treatment control, augmented psychosocial treatment (PT/ACBT) and combined medication and PT/ACBT) for non-responders to the BEI treatment. Adolescents who do not respond to the BEI and are randomized to the intervention arms of (PT/ACBT) or combined intervention (PT/ACBT+MED) will show differential improvements in primary and secondary outcomes (see Table 5). We hypothesize that relative to the no treatment control group, both groups will show improvements, with the largest effects for those who receive PT/ACBT+MED. Secondary analyses will be conducted for the one-year follow-up assessment for all groups. It is expected that therapeutic gains will extend through the follow-up period. Secondary analyses of treatment-related changes in the associated variables listed above will examine whether these changes mediate improvements in substance use. Analyses

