Aim 3: The third aim is to determine if, given nonresponse to the BEI, it is preferable to augment treatment with enhanced psychosocial intervention or multimodal treatment. As previously stated, we expect less than 50% of the sample to respond to the BEI, leaving at least 150 treatment-resistant adolescents to be randomized into one of the three treatment arms: (1) No treatment, (2) PT/ACBT, (3) PT/ACBT + MED. Using the general linear modeling techniques as implemented by SAS PROC GLM, we will examine differences between the treatment arms over post-treatment and one year follow-up measurement points with fixed effects of treatment arm. Analyzing each time period will address separate questions about the effect of intervention immediately post-treatment and at one-year follow-up. For these analyses, mixed linear models and/or GEE strategies will be used (Hedeker et al., 2006). Primary and secondary outcome measures will be evaluated separately (see Table 5). As our sample size permits, as a secondary analysis, we will also examine whether changes in the secondary outcomes listed above following treatment mediate response to treatment and substance use during the follow up phase.

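### Aim 3 states no adjustment for use days before randomization and does not fix one primary model; adding the covariate and naming the model costs almost nothing

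*Combined protocol and SAP*

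**What the plan says.** - **Outcome** (Analyses, Aim 1): "We will calculate days of alcohol and marijuana use during the past 90-days using data from the Substance Use Questionnaire".
- **Aim 1 model:** "Repeated measures GLM techniques as implemented by SAS PROC GLM will be used", with age, ethnicity, family SES, gender and ADHD-related impairment as covariates.
- **Aim 3 model** (Analyses, Aim 3): it opens with "Using the general linear modeling techniques as implemented by SAS PROC GLM", applied to the post-treatment and one-year time points. Treatment arm is the only fixed effect listed. Two sentences later: "For these analyses, mixed linear models and/or GEE strategies will be used". No distribution, link or covariate is given.
- **Switch** (opening text of Analyses): normality, linearity, independence and equal variance are examined before outcomes are analysed. Then: "Should these assumptions not be met, we will adjust the analytical approach or use transformations as appropriate". No criterion and no named alternative follow.
- **Age:** the Interventions section makes age a covariate when response to treatment is evaluated. That text sits in the paragraph on the brief intervention, so its reach to Aim 3 is unclear.
- **Data available** (Table 5): the past-3-month SUQ is completed at 6, 9, 12, 15 and 18 months, which are all the points at which non-response can lead to randomization.

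**The concern.** Two gaps meet in Aim 3, the only randomized comparison in the study.

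First, use days before randomization are likely to predict use days afterwards. Leaving them out of the model leaves explainable variance in the error term, in arms of only about 42. The time points in the Aim 3 model are both after randomization, so the repeated-measures structure does not bring the earlier value in either.

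Second, an analyst could follow the text and fit PROC GLM, a mixed model, a GEE with any link, or something chosen after assumption checks. A bounded count may well fail a normality check, so the unspecified branch may be the one that is used. For Aim 1, many zeros are foreseeable from the plan itself. Entry does not require own use, because perceived peer use or family history can meet the substance-specific criterion. Also, "any marijuana use in adolescence is considered non-normative", the alcohol norm in Table 4 is zero at ages 12 to 14, and the plan expects that "approximately 50% of adolescents will show meaningful response to the BEI, as evidenced by no more than normative substance use".

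**Working it through.** **1. Inputs from the documents.** Aim 3 has 150 randomized, at most 15% dropout, three arms, effect size .40, stated power .90, two-sided alpha .05 (alpha and sidedness are stated for Aim 1). Remaining: 150 × .85 = 127.5, about 127, or about 42 per arm if allocation is equal (assumed).

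**2. The plan's own figure.** The closest match to .90 is a within-between interaction with 3 groups and 2 measurements, f = d/2 = .20, and r = .25 borrowed from the sentence on the medication interaction. Noncentrality = f² × N × m/(1 − r) = .04 × 127 × 2/.75 = 13.55, giving power .913. The plan does not state this variant. One pairwise comparison at d = .40 with about 42 per arm has power of about .45.

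**3. What a baseline covariate does in normal theory.** The effective effect size becomes d/√(1 − r²). Normal approximation, pairwise, 127/3 per arm:

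| Correlation r | Effective d | Power |
|---|---|---|
| none used | .400 | .452 |
| .25 | .400/√.9375 = .413 | .476 |
| .50 | .400/√.75 = .462 | .566 |

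**4. The same question with skewed counts.** The documents give no mean, dispersion or zero share for days of use, so these are assumed: gamma-Poisson counts capped at 90, latent pre-post correlation .5, 42 per arm, 800 runs per row. Gamma var. is the assumed variance of the heterogeneity between adolescents. All three tests in the table use days of use; ANCOVA adds the earlier use days.

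| Mean, gamma var. | Scenario | t-test, raw days | ANCOVA, raw days | ANCOVA, log(1+days) |
|---|---|---|---|---|
| 10, 1 | rate halved | .821 | .860 | .801 |
| 10, 2 | rate halved | .561 | .612 | .522 |
| 20, 1.5 | rate halved | .679 | .744 | .628 |
| 10, 1 | 20% extra zeros, rate halved | .646 | .690 | .472 |
| 10, 2 | 20% extra zeros, rate halved | .402 | .440 | .294 |
| 20, 1.5 | 20% extra zeros, rate halved | .500 | .534 | .334 |
| 10, 1 | abstinence only (20% to 45% extra zeros) | .239 | .255 | .458 |
| 10, 2 | abstinence only | .136 | .155 | .320 |
| 20, 1.5 | abstinence only | .199 | .194 | .431 |

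- *Gain from adjustment* (raw ANCOVA minus t-test): 3.4 to 6.5 points when the rate is halved, −0.5 to +1.9 when treatment acts through abstinence only. In separate runs with halved use days, the gain was about 3 to 7 points at a baseline correlation of .6 and about zero at .3.
- *Type I error* with no effect: t-test .045 to .055, raw ANCOVA .044 to .049.
- *Choice of scale* (raw minus log ANCOVA): from +5.9 (.860 − .801) to +21.8 points (.690 − .472) when the rate is halved, and from −16.5 (.155 − .320) to −23.7 (.194 − .431) under abstinence. The sign reverses.

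**5. Against a count model.** With lognormal heterogeneity, a negative-binomial model adjusted for log earlier days gained −1 to +9 points over raw ANCOVA after its size was corrected. Uncorrected, its type I error across all the null runs was .06 to .08.

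**The case against.** The best defence is that nothing in the plan is wrong as written. PROC GLM can carry a covariate, GEE can take a log link, and raw-scale tests held their size in simulation. The assumption checks are placed ahead of outcome analysis. All of that stands, and it limits the point to one missing covariate and missing detail.

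Two stronger readings are tempting, and the documents support neither.

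- **That PROC GLM costs power in Aim 3.** The zero-heavy argument belongs to Aim 1. Aim 3 takes only adolescents with recent non-normative use, and their later share of zeros is unknown. The simulated sign reverses with the way treatment works. Setting an unadjusted raw-days test against a baseline-adjusted count model would not settle it, because that mixes distribution with adjustment. In one set of gamma-Poisson runs with matched adjustment, raw ANCOVA had power .40/.68/.48/.68/.62 and a permutation negative-binomial test .40/.68/.46/.67/.59.
- **That the open switch removes error control.** Reporting the best of raw and log ANCOVA gave type I error of .07 to .08 in simulation, and the best of four tests .11 to .13. Those are upper bounds for picking the smallest p-value. The plan describes no such picking, and a choice made blind to arm would inflate less. But it does not require that blinding either, so the gap is worth closing.

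**Conclusion.** The point holds as a low-severity improvement. Aim 3 lists no covariate for use before randomization, although the data are already collected. It also names several models for one comparison, on top of the general permission that "we will adjust the analytical approach or use transformations as appropriate".

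The expected gain from the covariate is about 0 to 7 points of power with type I error held, under the assumed count distributions and about 42 per arm. It could be larger if the measured correlation is high: normal theory gives 11 points at r = .50 (.566 − .452), and one other assumed scenario gave 13 (.49 to .62). It could be nil if the correlation is weak or treatment acts through abstinence alone.

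No power loss from PROC GLM can be claimed. That no scale wins in every scenario is a reason to choose one in advance, not evidence that the named one is wrong.

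**What to change.** 1. In the Aim 3 model, add past-90-day alcohol and marijuana use days from the SUQ at the assessment that triggered randomization, and confirm that age is also a covariate there. Raw or log scale is acceptable. If log, use log(1+days), because randomization can be triggered by another drug and the alcohol and marijuana count can then be zero.
2. Reconcile the general Analyses text with the Aim 1 and Aim 3 paragraphs. For each aim, name one primary model, distribution and link, and one fallback with the condition that invokes it, before outcomes are examined by arm.
3. A log-link count model can be the primary or a sensitivity analysis. If used at this arm size, give it a permutation or small-sample-corrected p-value.

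The cost is plan wording and some programming, with no new data and no added burden on participants. The covariate uses one degree of freedom. If a count model becomes primary, the effect is reported as a rate ratio instead of a difference in mean days.

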Power Analysis: For Aim 1, previous evaluations of BEI report a large effect of treatment on days of alcohol use (d=2.67; Winters et al., 2007). A sample size of 300 (G*Power 3.1.2 software), with alpha of 0.05 for a two-tailed test, will provide power = 0.96 to detect a small treatment effect size of 0.25 if there are no drop outs. Assuming a maximum dropout rate of 15%, as shown in previous studies with Hispanic adolescents with behavior problems (Pantin et al., 2009; Prado et al., 2007), the power drops slightly to 0.90. We also plan to measure the impact of concurrent medication use on treatment effect. For this analysis there are now two groups of participants, those currently using stimulant medication and those not using stimulant medication. The sample size of 300 with a maximum drop-out rate of 15% will provide .90 power to detect an interaction effect of medication, assuming a small pre-test to post-test correlation among measures (r = .25). For Aim 3, a sample size of 150 with a maximum drop-out rate of 15% will provide .90 power for a treatment effect size of .40, which is adequate considering that most ES for similar treatments range between .40 and .80 (Waldron & Turner, 2008). Thus, the sample should be sufficient to detect significant effects of treatment as well possible prediction models.

c. Potential Risks

Risk: Participants may experience mild and transitory psychological discomfort from completing research measures that deal with emotionally laden material, including reporting on illicit drug use and other antisocial or illegal behaviors, which may be uncomfortable for some participants. **Procedure:** We will inform participants of the NIH Confidentiality Certificate prior to collecting any data for the study, which will shield the research data from a subpoena or court order. In addition, participants and their parents will be advised to ask questions of study personnel if confidentiality is of a concern, and to refrain from answering questions that cause them personal distress.

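### Aim 2 defines response as use status at 6 months but tests its predictors on change in days of use, which may mask or reverse the hypothesised direction

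*Combined protocol and SAP*

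**What the plan says.** In Hypotheses and Data Analysis, the Aim 1 statement defines meaningful response as a status, "as evidenced by no more than normative substance use assessed at 6-months following treatment". Research Design and Methods defines non-response the same way, as use above the norms in the past 90 days. The Aim 2 hypothesis is directional: "It is expected that poor response to treatment will be associated with high ADHD symptomatology, concurrent delinquency", followed by further risk factors.

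The Analyses section tests something else. For Aim 1, "Repeated measures GLM techniques as implemented by SAS PROC GLM will be used", to see whether "substance use outcomes decrease significantly from baseline to 6-month assessment". The outcome is a count: "We will calculate days of alcohol and marijuana use during the past 90-days using data from the Substance Use Questionnaire". The covariates are listed: "Several control variables (age, ethnicity, family SES, gender, and functional impairment associated with ADHD) will be entered into the model as covariates". Intake use is not among them, because it is one of the two repeated outcomes. Aim 2 then takes over this model: "Using the GLM as described above, we will investigate the impact of the covariates on substance use variables over time". A Cox model may also carry the Aim 2 terms, but only if it proves more sensitive. No sentence says which model term tests a predictor.

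**The concern.** Aim 2 asks which teens fail the BEI. The hypothesis concerns where they stand at 6 months; the analysis concerns how many days of use they have lost since intake. The two can disagree. The listed predictors are plausible correlates of use, so teens who score high on them may start with more days and have more to lose. A teen who falls from many days to fewer can show a large improvement and still be a non-responder. Teens who do not use at intake, whom the Participants criteria admit, cannot fall at all.

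At stake is the direction of the Aim 2 conclusion: a risk factor could be reported as unrelated to response, or as favourable, although it goes with more non-response at 6 months.

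**Working it through.** **Inputs.** From Power Analysis: two-sided alpha .05; N = 300, less 15% dropout = 255; pre-post correlation r = .25. That r is given only for the medication interaction ("assuming a small pre-test to post-test correlation among measures (r = .25"), so using it here is an assumption. The documents do not give the predictors' correlations with use, the share of intake non-users or the size of the fall. These are assumed below.

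**1. The plan's own figure.** Aim 2 has none, so I checked the Aim 1 contrast it builds on. With d = .25 and r = .25, dz = .25/√(2 × .75) = .204. Paired-t power is .941 at N = 300 (stated .96) and .901 at N = 255 (stated .90). The second figure agrees and the first is close.

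**2. What the test is.** With two time points, predictor-by-time is the slope of (6-month minus intake days) on the predictor. Let a and b be the predictor's correlations with intake and 6-month use, and s0 and s6 the SDs of use. The slope per SD of predictor is b·s6 − a·s0. With equal SDs this is b − a, in SD units. The intake-adjusted slope is (b − a·r)/(1 − a²).

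**3. When the signs oppose.** This happens when a·r < b < a, that is r < b/a < 1. Example with a = .40, b = .20, r = .25: change gives .20 − .40 = −.20 SD (favourable); adjusted gives (.20 − .10)/(1 − .16) = +.12 SD (adverse).

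**4. How often.** corr(predictor, change) = (b − a)/√(2(1 − r)). Partial correlation given intake use = (b − a·r)/√((1 − a²)(1 − r²)). Noncentral t, N = 255, a = .30, r = .25, equal SDs:

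| b | corr. with change | change test: better | change test: worse | partial r | adjusted test: worse |
|---|---|---|---|---|---|
| .075 (only through intake use) | −.184 | 84% | under 0.1% | 0 | 2.5% |
| .20 | −.082 | 26% | 0.1% | .135 | 58% |
| .25 | −.041 | 9.5% | 0.5% | .19 | 87% |
| .30 | 0 | 2.5% | 2.5% | .24 | 98% |
| .40 | +.082 | 0.1% | 26% | .35 | over 99% |

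For predictors acting only through intake use (b = a·r), with a from .2 to .4, the change test says better in 50–98% of trials at r = .25, 36–90% at r = .5 and 23–70% at r = .7.

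**5. Proportional falls.** Here the SDs are unequal. If everyone halves their use and b = a, the slope is .5·a·s0 − a·s0 = −.5·a·s0, which is negative although no one responded differently in relative terms. Simulated overdispersed counts, N = 255, 2,000 runs, predictor correlated about .34 with intake days (except the last row):

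| Assumed scenario | slope, days per SD | better | worse | corr. with non-response |
|---|---|---|---|---|
| Equal 50% fall | −1.71 | 86% | 0% | +.31 |
| 50% fall, higher risk falls less (+0.15 log units per SD) | −0.96 | 44% | 0% | +.38 |
| 50% fall, higher risk falls much less (+0.35) | +0.22 | 3% | 11% | +.46 |
| 20% fall, higher risk falls less | +0.44 | 1% | 17% | +.40 |
| No average change, stable link | 0.00 | 6% | 5% | +.32 |
| No average fall, link half as strong at 6 months | −1.90 | 87% | 0% | +.17 |
| 20% rise | +0.62 | 0% | 18% | +.32 |
| 50% fall, predictor unrelated to intake use | −0.01 | 3% | 2% | 0 |

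**6. Intake non-users.** With a binary predictor, and new use assumed in 5% of lower-risk and 20% of higher-risk non-users, the change test says better as follows. With 50% non-users: 100% of runs at a 50% fall, 68% at a 20% fall and 2% with no fall among users. With 80% non-users: 48%, 6% and 0%.

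**The case against.** - **The direction is conditional.** A reader might infer that risk factors will generally look favourable, or that the test has almost no chance of finding an adverse predictor. The documents support neither. ADHD symptoms, parental monitoring and deviant peers may be persistent. If their correlation with use stays at .30, the change test is unbiased; if it rises to .40 with r = .7, the test flags the predictor as adverse 54% of the time. Regression to the mean does not by itself bias a stable predictor, and non-users can start using, which pushes the slope in the hypothesised direction. This stands, and it limits the claim to 'may mask or reverse'.
- **The plan has other routes.** The Cox analysis of maintaining normative use models the response concept and lacks this artefact. The Analyses section also promises assumption checks and transformations, and on a log scale an equal proportional fall becomes a constant shift. But the Cox option is a conditional addition, the transformation is unspecified, and neither is tied to the Aim 2 hypothesis.
- **Days are a documented response measure.** The Interventions section lists days of use among the measures for evaluating treatment response. That justifies analysing days, but the Aim 2 hypothesis follows directly on a definition by status.
- **The tested term is inferred.** The plan never writes predictor-by-time. The other candidate, the between-subject effect, averages intake and 6-month use and does not test response either.
- **Conditioning is not neutral.** For predictors that are not randomised, change and conditional models answer different questions. With a = b = .30 and r = .25 there is no differential change, yet the conditional test says adverse 98% of the time. So the documents do not support calling the change analysis invalid; it needs a label.

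**Conclusion.** The concern holds in conditional form. That the defined response and the tested quantity differ, and that intake use is not a listed covariate, is in the text and needs no assumed figures. Reading the test as predictor-by-time is an inference from the plan's wording, though the natural one.

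Whether the result is misleading depends on unknowns. Masking or reversal is likeliest when use falls roughly in proportion to its starting level, which is one way Aim 1 could succeed, or when the predictor's link with use weakens by 6 months. There is no reversal if use is flat or rising with a stable predictor, if the adverse effect is strong relative to the average fall, or if the predictor is unrelated to intake use. It is weak when most teens are non-users and the fall is small. At a = .30 and r = .25 the rate of false favourable findings runs from 84% (b = .075) through 9.5% (b = .25) to the nominal 2.5% (b = .30). These figures illustrate and do not forecast.

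The point concerns prediction in the single-arm stage and does not touch the randomised Aim 3 comparison.

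**What to change.** In Analyses, Aim 2:

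1. Make the main analysis a logistic regression of 6-month response status (normative or non-normative use, as the plan defines it) on intake values of the predictors, with the plan's covariates. Report it with and without intake use in the model.
2. For days of use, add a model of 6-month days conditional on intake days, suited to counts.
3. State which coefficient tests each predictor.
4. Keep the predictor-by-time analysis, if wanted, as secondary, described as addressing change in days and not response.

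The cost is wording. Table 5 already schedules the Substance Use Questionnaire at intake and 6 months, and the 6-month status is measured before any second-stage randomisation. There are two downsides. A binary outcome carries less information than days, which item 2 partly offsets. The conditional and change models can also differ for predictors that are not randomised, so the report should say which question each one answers.
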